## Hypotheses

Researchers' primary hypothesis is that participants randomized to the popular online content loneliness SSI (*the Lonely Blu Surfer program*) will have greater reductions in loneliness between baseline and 8-week follow-up than those who are randomized to the active control condition (*the Sharing Feelings program*).

As secondary hypotheses, researchers predict greater improvements in distress, general self-efficacy, hopelessness, meaning and purpose in life, and adaptive actions and thoughts in the popular online content loneliness SSI condition relative to the researcher created SSI condition. Researchers also predict that participants who are randomized to the popular online content SSI (*the Lonely Blu Surfer program*) will report greater reductions in loneliness than those randomized to the researcher-created loneliness SSI (*the Overcoming Loneliness program*).

### *Exploratory hypotheses*

1. Demographics and baseline mental health characteristics predict one's willingness to choose a certain kind of content.
2. The kinds of content one chooses predict change in loneliness between baseline and 8-week follow-up.
3. Younger participants will experience a greater reduction in loneliness after the popular online content interventions than older participants at 8 weeks.
4. The popular online content SSI condition (the *Lonely Blu Surfer* program) is more likely to lead to an insight experience than the researcher-created SSI (*Overcoming Loneliness* program) condition.
5. Having an insight experience during an intervention is associated with greater improvement in loneliness at 8 weeks.
6. Higher baseline general self-efficacy is associated with greater improvement in loneliness at 8 weeks.
7. Engagement with the researcher-created SSI predicts greater improvement in loneliness at 8 weeks.
8. Engagement with the popular online content SSI predicts greater improvement in loneliness at 8 weeks.

## **Analysis Plan**

### *Main analysis*

The main DV is change in loneliness (UCLA Loneliness Scale - 20 item Version 3) from baseline to 8-week follow-up. The main analysis compares change in loneliness from baseline to 8-week follow-up across experimental conditions. Researchers will use a mixed-effects model predicting distress with condition, measurement time point (1 = baseline, 2 = 4-week follow-up, 3= 8-week follow-up), and the 2-way interaction between condition and measurement time point as IVs and a participant identifier as a random intercept. Using the “lme4” package in R, these analyses will take the following form:

`lmer(loneliness ~ time*condition + (1|study_id))`

### *Secondary analysis*

Researchers will re-run the main analysis separately for each secondary outcome, although the timepoints measured by the “time” variable will differ across outcomes (see table 5).

#### *Inclusion criteria*

Main analyses will be limited to only those participants who 1) met criteria for struggling with loneliness, 2) were randomized to a condition (ie, those who consented to participate and completed the baseline measures), 3) did not indicate that they did not participate seriously at the end of the study, 4) completed the study only once, and 5) were not clearly bots, responding mischievously, or speeding past most of the content. Researchers will examine whether a response is fraudulent on a case-by-case basis, taking the suspicious factors mentioned in study 1’s inclusion criteria into account.

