## **Inclusion criteria**

Researchers will limit the main analyses to only those participants who 1) meet criteria for struggling with loneliness, 2) are randomized to a condition in analyses (ie, those who consented to participate and completed the baseline measures), 3) did not indicate that they did not participate seriously at the end of the study, 4) completed the study only once, and 5) spent at least 3 minutes completing the study introduction and baseline measures (ie, were not clearly bots or speeding past most of the content).

Update February 20, 2023:

Due to many suspected bots and scammers taking the survey (particularly from 12/22/2022 to 1/22/2023), researchers identified an array of suspicious factors suggesting that the same person may have taken the survey multiple times or that some form of automated bot was used to complete the survey. Based on these criteria, researchers decided to add an

additional column to the dataset with a suspicion score for each response and another column indicating whether researchers consider the response as fraudulent, real, or likely fraudulent.

The factors that researchers identified as suspicious are as follow:

- Using windows NT 6
- Using android 9 or below
- Multiple IP Addresses with same first 8 digits, particularly when taken within a close time period
- Reporting that one found the study on facebook, Instagram, or Twitter after Dec 10, 2022 or Reddit after Jan 13, 2023
- Email address contains 6 numbers in a row and is from gmail
- Responses to the question about what they liked and what they would change about the intervention are specific and identical
- Reports one found the study on Researchmatch, but one is not on the Researchmatch email list
- Many participants completing each study session within a short amount of time, often using similar devices
- duration < 8 minutes if finished whole survey
- more than 5 responses with the exact same longitude and latitude, many have >20 or 30
- Researchers emailed suspected bots/scammers and asked them to indicate where they found the study and what they learned from participating in the study. In suspicious responses, one's email address did not match one's stated name, emails used broken English, and some email responses were highly similar to others. Many who took the survey within a few minutes of one another also replied to the emails within a few minutes of one another.

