## Materials

The experimental condition will be the *Blu Surfer* Program, a 25-minute SSI that the research team developed centered on popular online content relevant to mental health. In the SSI, each user is first asked to select the kinds of support they would like to view. Next, the user is asked to explore a library of annotated popular online content (filtered by the kinds of support they chose) and to select the content they find personally valuable. Researchers crowdsourced this library by asking people from a range of online communities and an undergraduate psychology course lecture to contribute one piece of popular online content that they believed could help someone overcome a difficult time or mental health challenge in their life. Finally, the SSI provides the user a list of the content they selected to keep and draw from, build on, or share with friends.

The active comparison condition will be the *ABC (Action Brings Change) Project* (TEAM Lab Version). The original *ABC Project* is a 30-minute SSI for teens based on behavioral activation that was found to be efficacious for reducing depression, anxiety, hopelessness, and self-hate and increasing perceived control and agency in youth (link to SSI: <https://osf.io/ch2tg/>, license: <http://creativecommons.org/licenses/by-nc-sa/4.0/>). The TEAM Lab version slightly modifies the intervention to make it more relevant to both teens and adults.

The third condition is *online help-seeking as usual*, which aims to emulate how one might find support using the internet on one's own. In this condition, participants are asked to browse the internet for 25 minutes to find popular online content for overcoming personal problems and create an annotated list of links to the content they find personally useful. This condition is similar to the “self-study” condition in another study that found self-study and a video intervention equally increased mental health knowledge (Yamaguchi et al., 2019). The survey platform provides text entry boxes to help each participants create their guide and then provides a text version of their guide for them to keep.

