### *Inclusion criteria*

Main analyses will be limited to only those participants who 1) met criteria for struggling with distress, 2) were randomized to a condition (ie, those who consented to participate and completed the baseline measures), 3) did not indicate that they did not participate seriously at the end of the study, 4) completed the study only once, and 5) were not clearly bots, responding mischievously,

or speeding past most of the content. Researchers will examine whether a response is fraudulent on a case-by-case basis, taking the suspicious factors mentioned in study 1's inclusion criteria into account.

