#### *Additional analyses*

1. Duplicate the main analysis with the subset of participants who did not meet criteria for struggling with loneliness and thereby participated in the study without being compensated.

2. Duplicate the main analysis comparing the change in loneliness from baseline to week 4 follow-up rather than to week 8.
3. Duplicate the main analysis with the subset of participants who completed the week 8 follow-up.
4. Duplicate the main analysis but with the following covariates included in the mixed-effects model: gender (multiple choice), age (continuous), ethnicity (categorical), sexual orientation (categorical), education level (categorical), socioeconomic status (continuous), and if participants completed the study on a computer, tablet, or phone.
5. Use a one-way ANOVA to test between-group differences in loneliness at 8-week follow-up. If the omnibus ANOVA produces a significant F-score, researchers will conduct two planned contrasts to compare the experimental condition to each other condition, and will compute Cohen's ds of these comparisons. Researchers will run the same ANOVA on the 4-week follow-up data and at post-intervention for outcomes collected then. Researchers will also conduct these ANOVAs on secondary outcomes.
6. Calculate Cohen's d effect sizes reflecting within-group intervention effects on loneliness for each condition from baseline to 4-week and 8-week follow-ups.
7. Researchers will run four logistic regression models with dropout as the outcome baseline measures as predictors to determine if they predict which participants drop out either before completing the intervention, before the post-intervention questions, or before the 4- and 8-week follow-ups.
8. Duplicate the main analysis including data from suspected bots/scammers.

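### Studies 2 and 3 replace Study 1's pre-randomisation 3-minute rule with an undefined, unmasked judgement, so behaviour that depends on the arm can affect who is in the main analysis

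*Combined protocol and SAP*

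**What the plan says.** Study 1 (Aim 1, Inclusion criteria, criterion 5) keeps those who "spent at least 3 minutes completing the study introduction and baseline measures (ie, were not clearly bots or speeding past most of the content". The rule is the time limit; the words in brackets explain it.

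Study 3 (Inclusion criteria, criterion 5) has no time limit and no restriction to baseline pages. It keeps those who "were not clearly bots, responding mischievously, or speeding past most of the content". Study 2 uses the same words. Both then say that fraud is judged case by case, taking into account the suspicious factors listed for Study 1.

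Both studies describe the randomised as people who "were randomized to a condition (ie, those who consented to participate and completed the baseline measures", so the introduction and baseline measures come before allocation and the assigned program comes after it.

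In Study 2 (Materials) the tasks differ. ABC adapts a program whose original version lasts 30 minutes. Blu Surfer is a 25-minute library that users filter and sample. In the third condition "participants are asked to browse the internet for 25 minutes to find popular online content".

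Item 8 of Additional analyses in both studies reads: "Duplicate the main analysis including data from suspected bots/scammers".

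**The concern.** A speed limit on pages seen before allocation cannot depend on arm. A judgement about speed or sincerity over unspecified content may draw on the assigned program. If low-effort participants are easier to spot in one arm, they are removed at different rates from the population that tests the hypotheses. The arm that loses more of them then looks better than it is, and the comparison drifts from all eligible randomised participants towards those who engaged. A reviewer who knows the arm or the outcome adds a second route to the same problem. This bias does not shrink as the sample grows.

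**Working it through.** **Step 1: what enters the decision, before or after randomisation.**

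- Study 1, criterion 5: time on the introduction and baseline measures. Before.
- Studies 2 and 3, criterion 5: speed over most of the content, with *content* undefined; mischievous responding, also undefined. Could be either.
- Factors imported from Study 1's list: device, IP address, location, email pattern and recruitment source do not depend on arm. Total duration under 8 minutes among those who finish the survey includes time in the assigned program, so it arises after randomisation. So does identical feedback on what participants liked or would change about the intervention, and so do email replies on what they learned. The last two can also reveal the arm.
- Cut-off for speeding, masking to arm or outcome, and timing of the decision: none stated for Studies 2 and 3.

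Post-randomisation information can therefore enter the decision under the plan as written.

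**Step 2: does an existing safeguard cover it?** Item 8 restores suspected bots and scammers. Human speeders and mischievous responders are not named. The differential-dropout checks under Missing data handling concern participants who leave, not participants whom the researchers remove. Reporting exclusions by arm is not planned.

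**Step 3: size.** The documents give no exclusion rate, effect size, SD or sample size, so there is no figure to reproduce and every input below is an assumption.

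*Illustration A.* A share L of each arm is low-effort and improves 0.5 SD less; a fraction d of these is detected and removed. The low-effort share left is L(1 − d)/(1 − Ld).

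- L = 0.10: with d = 0.80, 0.02/0.92 = 0.022; with d = 0.20, 0.08/0.98 = 0.082. Difference 0.060 × 0.5 = 0.030 SD.
- L = 0.20: with d = 0.80, 0.04/0.84 = 0.048; with d = 0.20, 0.16/0.96 = 0.167. Difference 0.119 × 0.5 = 0.060 SD.

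The 80% against 20% detection contrasts a program delivered in the survey with browsing outside it. That is Study 2's secondary comparison with help-seeking.

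*Illustration B.* The true effect is zero, engagement is standard normal with correlation r to improvement, and the lowest fraction q is removed in each arm. The mean shift in an arm is r·φ(z_q)/(1 − q), and the bias is the difference between arms. Type I error is for a two-sided 0.05 z-test (the plan does not state sidedness), with 100 to 400 randomised per arm and r from 0.1 to 0.3.

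| Removed, arm 1 vs arm 2 | Bias (SD) | Type I error |
|---|---|---|
| 5% vs 5% | 0 | 0.050 |
| 5% vs 10% | 0.009–0.026 | 0.050–0.064 |
| 5% vs 20% | 0.024–0.072 | 0.053–0.159 |
| 10% vs 30% | 0.030–0.091 | 0.054–0.206 |

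The bias is small unless removal differs clearly between arms. With a rule based only on pre-randomisation data, expected removal is equal and the bias is zero, as in the first row.

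**The case against.** Several points on the other side stand.

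- In Study 1 the speeding phrase only explains the baseline rule, and Studies 2 and 3 may simply have carried it over. A reader might infer that arm-specific behaviour *decides* who is analysed. The text supports only that it *can*, because *content* is undefined.
- A reader might apply 0.03–0.06 SD to the primary hypotheses. It does not apply there. Study 2's primary contrast is Blu Surfer against ABC, where the detection gap may be smaller; if ABC is the better-observed arm, the bias would run against the study's own hypothesis. Study 3 has no off-platform arm, and its programs have similar nominal lengths.
- Help-seeking is not unobserved: participants enter an annotated list in the survey, and the items are counted.
- A reader might take Study 1 to be free of post-randomisation selection. It is not. It also excludes people who say at the end that they did not take part seriously, and its February 2023 update introduced the same fraud factors, though as flags in the dataset without a stated exclusion rule. The contrast holds for criterion 5 only.
- Item 8 could be read as restoring some speeders, because short duration is among the fraud factors. It does not clearly do so.
- Study 1 met many suspected bots even with its 3-minute rule, so stripping all intervention signals from the fraud review would give up real evidence of fraud.

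None of this supplies the missing definition or masking. It narrows the claim and shapes the remedy.

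**Conclusion.** The point holds as a possibility left open by the plan, not as a demonstrated bias. Criterion 5 in Studies 2 and 3 is discretionary, has no stated masking, and can draw on data arising after randomisation. The risk is clearest in Study 2, where the tasks differ in kind; in Study 3 it is plausible but not shown. A shift of about 0.03–0.06 SD rests wholly on assumed inputs (10–20% low-effort, 0.5 SD less improvement, 80% against 20% detection) and illustrates Study 2's secondary contrast with help-seeking. For the primary contrasts the documents fix neither the size nor the direction. This is a cheap improvement worth making, not a flaw that undermines either study.

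**What to change.** 1. In the Inclusion criteria of Studies 2 and 3, define speeding for the main analysis by Study 1's rule, so that those kept "spent at least 3 minutes completing the study introduction and baseline measures". Judge mischievous responding on baseline data only.
2. Keep the fraud review, but have it done before the outcome analysis by reviewers masked to arm and to the 4- and 8-week outcomes. Use first the factors that do not depend on arm: device, IP address, location, email pattern, recruitment source and duplicates. Use intervention-related signals, such as identical feedback, only in a form that does not show the arm.
3. Report exclusions by arm and reason.
4. Widen item 8 of Additional analyses to restore everyone excluded under criterion 5, and add a re-run that removes speeders and mischievous responders.

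The cost is SAP wording, a masked data export, a table of exclusions and one extra re-run. The downside is that some people who skim the program, and possibly a few fraudulent records, stay in the main analysis and dilute the effect slightly. The re-run that removes speeders and mischievous responders shows how far they matter.

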#### *Missing data handling*

Although researchers will take efforts to avoid missing data (e.g., a financial incentive for completing the study and reminder emails), it is not necessary to impute missing data before performing a longitudinal mixed-model analysis (Twisk et al., 2013). Participants with missing data at some assessments will be included in the analysis and results will be modeled on the basis of the available data. For all analyses, the standard  $p < 0.05$  criterion will be used to determine statistical significance.

To test for faulty randomization, researchers will use chi-squared tests on demographic and outcome variables with Yates's continuity correction and t-tests with Welch's approximation of degrees of freedom and assuming unequal variance. If any faulty randomization effects are found, researchers will adjust for them using the confounding variable as a covariate in model testing and will consider them in interpretation of results. These tests will also be used to check for differential dropout.

#### *Additional analyses*

1. Duplicate the main analysis with the subset of participants who did not meet criteria for struggling with loneliness and thereby participated in the study without being compensated.

2. Duplicate the main analysis comparing the change in loneliness from baseline to week 4 follow-up rather than to week 8.
3. Duplicate the main analysis with the subset of participants who completed the week 8 follow-up.
4. Duplicate the main analysis but with the following covariates included in the mixed-effects model: gender (multiple choice), age (continuous), ethnicity (categorical), sexual orientation (categorical), education level (categorical), socioeconomic status (continuous), and if participants completed the study on a computer, tablet, or phone.
5. Use a one-way ANOVA to test between-group differences in loneliness at 8-week follow-up. If the omnibus ANOVA produces a significant F-score, researchers will conduct two planned contrasts to compare the experimental condition to each other condition, and will compute Cohen's ds of these comparisons. Researchers will run the same ANOVA on the 4-week follow-up data and at post-intervention for outcomes collected then. Researchers will also conduct these ANOVAs on secondary outcomes.
6. Calculate Cohen's d effect sizes reflecting within-group intervention effects on loneliness for each condition from baseline to 4-week and 8-week follow-ups.
7. Researchers will run four logistic regression models with dropout as the outcome baseline measures as predictors to determine if they predict which participants drop out either before completing the intervention, before the post-intervention questions, or before the 4- and 8-week follow-ups.
8. Duplicate the main analysis including data from suspected bots/scammers.

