#### *Additional analyses*

1. Researchers will duplicate the main analysis with the subset of participants who did not meet criteria for struggling with loneliness and thereby participated in the study without being compensated.
2. Researchers will duplicate the main analysis with the subset of participants who completed the week 8 follow-up.
3. Researchers will duplicate the main analysis but will include the following covariates in the mixed-effects model: gender (multiple choice), age (continuous), ethnicity (categorical), sexual orientation (categorical), education level (categorical), socioeconomic status (continuous), if participants completed the study on a computer, tablet, or phone, and whether participants answered at least one written-response question.
4. Researchers will use a one-way ANOVA to test between-group differences in loneliness at 8-week follow-up. If the omnibus ANOVA produces a significant F-score, researchers will conduct two planned contrasts to compare the experimental condition to each other condition, and will compute Cohen's ds of these comparisons. Researchers will run the same ANOVA on the 4-week follow-up data. Researchers will also conduct these ANOVAs on secondary outcomes and at post-intervention for outcomes collected then.
5. Researchers will calculate Cohen's d effect sizes reflecting within-group intervention effects on the loneliness for each condition from baseline to 4-week and 8-week follow-ups. They will also do so for each secondary DV

6. Researchers will run four logistic regression models with dropout as the outcome baseline measures as predictors to determine if they predict which participants drop out either before completing the intervention, before the post-intervention questions, or before the 4- and 8-week follow-ups.

*Additional analyses testing exploratory hypotheses*

1. To compare change in mental health outcomes across presence of an insight experience, researchers will conduct a mixed-effects model with loneliness as the outcome, timepoint, insight experience, and the interaction between the two as predictors, and a participant identifier nested within experimental condition as a random intercept.

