#### *Additional analyses*

1. Duplicate the main analysis with the subset of participants who did not meet criteria for struggling with distress and thereby participated in the study without being compensated.
2. Duplicate the main analysis comparing the change in distress from baseline to week 4 follow-up rather than to week 8.
3. Duplicate the main analysis with the subset of participants who completed the week 8 follow-up.
4. Duplicate the main analysis but with the following covariates included in the mixed-effects model: gender (multiple choice), age (continuous), ethnicity (categorical), sexual orientation (categorical), education level (categorical), socioeconomic status (continuous), and if participants completed the study on a computer, tablet, or phone.
5. Use a one-way ANOVA to test between-group differences in distress at 8-week follow-up. If the omnibus ANOVA produces a significant F-score, researchers will conduct two planned contrasts to compare the experimental condition to each other condition, and will

compute Cohen's ds of these comparisons. Researchers will run the same ANOVA on the 4-week follow-up data and at post-intervention for outcomes collected then. Researchers will also conduct these ANOVAs on secondary outcomes.

6. Calculate Cohen's d effect sizes reflecting within-group intervention effects on distress for each condition from baseline to 4-week and 8-week follow-ups.
7. Run four logistic regression models with dropout as the outcome baseline measures as predictors to determine if they predict which participants drop out either before completing the intervention, before the post-intervention questions, or before the 4- and 8-week follow-ups.
8. Duplicate the main analysis including data from suspected bots/scammers.

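### In all three studies the only planned standardised between-arm effects at weeks 4 and 8 come from single-visit ANOVAs on observed cases, so dropout that works differently by arm can bias the reported Cohen's d; the primary test is not affected

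*Combined protocol and SAP*

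**What the plan says.** Study 3, Additional analyses, item 5: "Use a one-way ANOVA to test between-group differences in loneliness at 8-week follow-up". If the omnibus F is significant, the researchers will "conduct two planned contrasts to compare the experimental condition to each other condition, and will compute Cohen's ds of these comparisons". The same ANOVA is run at week 4 and, for outcomes collected then, at post-intervention. It extends further: "Researchers will also conduct these ANOVAs on secondary outcomes".

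Study 2, Additional analyses, item 5 has the same rule for distress ("Use a one-way ANOVA to test between-group differences in distress at 8-week follow-up"). So does Study 1, item 4 ("Researchers will use a one-way ANOVA to test between-group differences in loneliness at 8-week follow-up").

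The other planned effect size is within arms only. In Study 3, item 6, it reads: "Calculate Cohen's d effect sizes reflecting within-group intervention effects on loneliness for each condition from baseline to 4-week and 8-week follow-ups".

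The main analysis in each study is a random-intercept mixed model with condition, time and their interaction. No standardised effect is specified from it. Studies 2 and 3 number the visits 1, 2 and 3 without saying whether time is a factor or a number. Study 1 gives no coding.

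The Missing data handling section of each study says that "it is not necessary to impute missing data before performing a longitudinal mixed-model analysis", and then: "Participants with missing data at some assessments will be included in the analysis". It states no rule for the single-visit ANOVAs.

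**The concern.** The mixed model can use the baseline and week-4 scores of someone who misses week 8. A one-way ANOVA on the week-8 score cannot: that person has no outcome and drops out of the test and of the d. The reason given for leaving missing data alone therefore does not reach the analysis that produces the between-arm ds.

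The two analyses also estimate different things. The main outcome is change from baseline, using all available data. The ANOVA d is a difference in level among those who answered at that visit.

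Readers and meta-analysts tend to pick up a Cohen's d. If lonelier or more distressed people leave one arm but not the other, that d will show a difference made by who stayed, and it may disagree with the primary model.

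**Working it through.** **No planned figure to reproduce.** The documents give no dropout rate, SD, visit correlation or expected effect. Every input below is an assumption.

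**Why the ANOVA d moves.** Work in SD units. Let r be the correlation between weeks 4 and 8, and let s be the shift in mean week-4 score among those still observed at week 8. If dropout depends on the week-4 score, the observed week-8 mean is off by about r × s in each arm, so

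bias in d ≈ r × (s in experimental arm − s in comparator).

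Equal shifts cancel; unequal shifts do not.

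**Simulation A: true effect 0.** 60,000 per arm; 30-50% week-8 dropout in both arms; random in one arm; log-odds of dropout rising 0.4-0.8 per SD of week-4 loneliness in the other; random-intercept model with time as a factor.

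| Visit correlations | ANOVA d | Mixed-model contrast |
|---|---|---|
| Equal, 0.5-0.8 | about -0.06 to -0.29 | within about 0.02 of 0 |
| Autoregressive | -0.06 to -0.28 | within 0.015 of 0 |
| Unequal: baseline-week 4 0.5, baseline-week 8 0.4, weeks 4-8 0.8 | -0.08 to -0.28 | -0.03 to -0.10 |

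A negative value flatters the arm that loses its lonelier members. The sign reverses if that is the comparator.

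**Why the last row is not zero.** A random intercept implies one common correlation c and predicts week 8 from baseline and week 4 with equal weights c/(1 + c).

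- Here the average correlation is (0.5 + 0.4 + 0.8)/3 = 0.567, so each weight is 0.567/1.567 = 0.362.
- The correct weights are (0.4 − 0.5 × 0.8)/(1 − 0.5²) = 0 for baseline and (0.8 − 0.5 × 0.4)/(1 − 0.5²) = 0.8 for week 4.
- Per SD of week-4 score the model predicts 0.362 × (0.5 + 1) = 0.543 instead of 0.8, leaving (0.8 − 0.543)/0.8 = 32% of the bias.
- 0.32 × (-0.08) = -0.03 and 0.32 × (-0.28) = -0.09, close to the simulated -0.03 to -0.10.

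**Simulation B: true week-8 d of -0.20.** Three arms, 6,000 per arm, mean of 3 runs, equal correlations, about 40% missing at week 8, missing at random. Monte Carlo error is about 0.02-0.03.

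| Who drops out | ANOVA d at correlation 0.5 / 0.7 / 0.8 | Mixed model at 0.5 / 0.7 / 0.8 |
|---|---|---|
| Completely random | -0.215 / -0.197 / -0.205 | -0.225 / -0.197 / -0.222 |
| By baseline, same rule in all arms | -0.207 / -0.221 / -0.199 | -0.188 / -0.211 / -0.199 |
| Later dropout by week 4, same rule in all arms | -0.211 / -0.226 / -0.219 | -0.187 / -0.210 / -0.203 |
| Lonelier leave, experimental arm only | -0.346 / -0.358 / -0.407 | -0.211 / -0.176 / -0.202 |
| Lonelier leave experimental, less lonely leave control | -0.482 / -0.571 / -0.638 | -0.184 / -0.208 / -0.227 |

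Under a common rule the largest departure of the ANOVA d is 0.226 − 0.200 = 0.026. In the last two rows it is 0.346/0.20 = 1.7 to 0.638/0.20 = 3.2 times the truth. Missingness in those rows was 0.40-0.43 in control and 0.39-0.40 in the experimental arm, so a comparison of dropout rates could see little.

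**The case against.** **No contradiction, and the primary test is safe.** A reader might infer that the plan breaks its own missing-data rule, or that the primary result is compromised. Neither is supported. The rule is tied to the mixed model, and the analysis it mentions is most naturally that model. The primary hypothesis is tested there, and it yields a between-arm difference in change in scale points from all available data. Only standardised effects are at issue, within additional analyses. This stands.

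**Not every between-arm d is affected in this way.** Item 5 also covers post-intervention measures, taken in the same session as the intervention, where attrition is a different matter. The ds are computed only after a significant F. This stands.

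**The plan already looks at dropout.** It checks for differential dropout, models dropout on baseline measures, and repeats the main model in week-8 completers. These help interpretation. But none has a stated consequence for d, the dropout models mention no arm interaction, and the completer analysis is itself restricted to completers. This stands only in part.

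**The size depends on a chosen mechanism.** A reader might infer that the d will be wrong. The documents do not show that: they give no dropout figures and no sign that dropout works differently by arm. The point is that the d can be biased, and that the plan has a better source for it.

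**The mixed model is not a complete cure.** It relies on missing at random and an adequate covariance, as the unequal-correlation row shows. It cannot repair dropout driven by unobserved scores, and the plan does not say that time is a factor. All of this stands.

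**Conclusion.** The point holds for the week-4 and week-8 Cohen's ds between arms in all three studies. They rest on participants observed at that visit, and the plan's reason for not imputing does not cover them.

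The bias is about -0.06 to -0.29 at a true effect of 0, if 30-50% are missing at week 8 and dropout follows earlier scores in one arm only. It is 0.03 or less in the scenarios where all arms share one dropout rule. Under missing at random, the mixed model with time as a factor comes within about 0.02 of zero when visits are equally correlated, and can be off by up to about -0.10 when they are markedly unequal. Rates, correlations and mechanisms are all assumed. This is a worthwhile correction to secondary reporting, not a flaw in the primary inference.

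**What to change.** In Study 1 item 4, Study 2 item 5 and Study 3 item 5 of Additional analyses:

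- For outcomes measured repeatedly, take the week-4 and week-8 between-arm differences in change from the mixed model already planned, with time stated to be a factor. Divide by the pooled baseline SD and report with 95% CIs.
- Keep ANOVA for the post-intervention measures.
- Label any week-4 or week-8 ANOVA ds that are retained as observed-case sensitivity results.
- In Missing data handling, say that the no-imputation rationale applies to the mixed models, and that it assumes missing at random.

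The cost is SAP wording and a little analysis work. No new data are needed, and the model is already to be fitted.
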